PROTOCOL FOR RESEARCH INVOLVING HUMAN SUBJECTS

**TITLE OF PROJECT: Cervical Spondylotic Myelopathy Surgical Trial (CSM-S Trial)
VERSION: 6.0, DATE: 12-17-24**

Study Sponsor: Patient-Centered Outcomes Research Institute (PCORI) & Alan and Jackie Stuart Spine Research Center

	Name	Signature	Email Address
Principal Investigator:	[name] MD		[contact]
Other Investigator(s):			
Correspondent			

Mailing Address:

[name]
[name]

[contact]
[contact]

II. DESCRIPTION OF STUDY

A. Purpose

1a. To determine if ventral surgery is associated with superior SF-36 PCS outcome at one year follow-up compared to dorsal (fusion or laminoplasty) surgery.

1b. To determine if, compared to pre-operative baseline status, both ventral and dorsal surgery for CSM improve symptoms of spinal cord dysfunction using mJOA.

2. To determine if, from a patient perspective, health resource utilization (out-of-pocket expenses and loss of productivity) for ventral surgery, dorsal fusion, and laminoplasty surgery are different.

3. To determine if cervical sagittal balance post-operatively is a significant predictor of SF-36 PCS outcome.

B. Background

Surgical decompression for CSM can improve its disabling symptoms, but surgical complications are common and many of these complications affect patients' overall health-related quality of life. The optimal surgical treatment, therefore, remains controversial, with disagreement between three main approaches: ventral decompression and fusion, dorsal decompression and fusion, or dorsal laminoplasty. This study aims to test the hypothesis that ventral surgery is associated with superior SF-36 PCS outcome at one year follow-up compared to dorsal approaches and that both ventral and dorsal surgery improve symptoms of spinal cord dysfunction using the mJOA score. A secondary hypothesis is that health resource utilization for ventral surgery, dorsal fusion, and laminoplasty surgery are different. A third hypothesis is that cervical sagittal balance post-operatively is a significant predictor of SF-36 PCS outcome.

C. Specific Location of Study

This is a multi-center trial. Subjects will be entered into the study from 10 separate centers.

D. Probable Duration of Project

Subjects will be recruited into the study over an 18 month period. All subjects will be followed for 5 years with clinical questionnaires.

E. Research Plan

1) Prospective, randomized multicenter trial. Approximately 159 randomized and 91 non-randomized patients would be recruited over 18 months with follow-up through 5 years.

2) Subjects (aged 45-80 years) with CSM (2 or more levels of spinal cord compression from C3 to C7) with 2 or more of the following symptoms/signs, clumsy hands, gait disturbance, hyperreflexia, up going toes, bladder dysfunction, or ankle clonus, will be treated with either ventral decompression/fusion, dorsal decompression with fusion, or dorsal laminoplasty. (Patients <45 years of age do not generally suffer from degenerative arthritis, which is why the lowest age of inclusion is 45).

3) Subjects with C2-C7 kyphosis $> 5^\circ$ (measured in standing neutral cervical spine radiograph), a segmental kyphotic deformity defined as 3 or more disc-osteophytes that extend dorsal to a C2-C7 dorsal-caudal line measured on cervical spine CT, structurally significant ossification of the posterior longitudinal ligament (OPLL), previous cervical spine surgery, or significant active health-related comorbidity (Anesthesia Class IV or higher) would be excluded from the study.

4) Each subject will be treated with either a Front Decompression/Fusion or Back of the Neck Decompression with fusion or Laminoplasty as part of standard clinical care. Decompression of the spinal canal to a diameter of at least 13 mm with restoration of cerebrospinal fluid flow around the spinal cord will be the goal, regardless of the approach. Surgical techniques have been standardized. Back of the neck decompression with fusion and laminoplasty are equivalent and preliminary evidence suggests that the outcomes are similar using the SF-36 PCS, which is the same questionnaire being used in this study (see table in Power Analysis section below).

5) Functional outcomes will be determined using well-known quantitative scales (SF-36, Oswestry Neck, mJOA, and EuroQol-5D). These instruments will be administered pre-op, 3 months, 6 months, and at 1 year. Additionally, functional outcomes instruments (SF-36, Oswestry Neck, and EuroQol-5D) will be collected annually at years 2,3,4 and 5.

6) Two independent neuroradiologists will review post-operative imaging at 3 months, and 1 year. Post-operative cervical spine MRI will be performed at 3 months to document satisfactory spinal cord decompression. Cervical spine

flexion-extension radiographs will be obtained pre-operatively on all patients and at one year after surgery to assess cervical fusion and/ or radiographic complications. Standing cervical-thoracic-lumbar-sacral films will be obtained on all patients pre-operatively and at one year postoperatively (post-operatively in the randomized group only) to assess cervical as well as overall sagittal balance. A cervical spine CT will be obtained on patients at 1 year who have an NDI score > 30 or whose plain films suggest instability.

7) A study coordinator will collect data at 30 days and at 1 year to document any complications or re-operations. Additionally, the study coordinator will assess whether the patient is having any swallowing complications following surgery.

8) Health resource utilization information (including out-of-pocket expenses) will be obtained using patient diaries along with copies of all medical bills and receipts at 1 month, 3 months, 6 months, and 12 months post-operatively for all of the patients. Participants also will be asked to keep track of days missed from work and days unable to perform usual activities, in addition to days missed from work for medical treatments or evaluations.

F. Data and Safety Monitoring Plan

- 1) All serious unexpected adverse events (e.g. death within 30 days of operation) will be reported to the IRB within 24 hours. Any appropriate funding agencies or regulatory agencies would be notified as well.
- 2) Any serious anticipated adverse event (e.g. wound infection, pulmonary embolus) will be reported to the IRB whenever their magnitude or frequency exceeds expectations.
- 3) All other adverse events (including loss of privacy, significant economic harm) will be reported to the IRB on an annual basis or at the time that re-approval is sought. Any adverse event judged unlikely or unrelated to the study will also be included in an annual report for the IRB.

G. Statistical Considerations

a. Specific data variables being collected for the study.

The data collection sheets will be submitted along with this protocol. There will be several data sheets as follows:

- 1) Screening/Baseline, 1 Month, 3 Months, 6 Months, and 1 Year Visit Checklist
- 2) Informed Consent Process
- 3) Inclusion/Exclusion Criteria
- 4) Baseline Demographics
- 5) Spine surgeon's data sheet

- 6) 30-day and 1 Year morbidity data sheet
- 7) 1 Month, 3 Months, 6 Months, 1 Year Return to Work Status
- 8) 3 Month Swallowing Evaluation
- 9) Initial Hospital Admission Data Sheet
- 10) 3 Months and 1 Year Radiology
- 11) End of Study
- 12) Adverse Event Form
- 13) Serious Adverse Event Report Form
- 14) Serious Adverse Event Follow-up Report Form
- 15) SF-36 questionnaires (pre-op, 3 months, 6 months, 1, 2, 3, 4, and 5 years),
- 16) Neck Disability Index questionnaires (pre-op, 3 months, 6 months, 1, 2, 3, 4, and 5 years)
- 17) mJOA, (pre-op, 3 months, 6 months, and 1 year)
- 18) EuroQol-5D (pre-op, 3 months, 6 months, 1, 2, 3, 4, and 5 years)
- 19) Health Resource Utilization Diary (1 month, 3 months, 6 months, 1 year)
- 20) Report of Second Cervical Surgery
- 21) Death Form
- 22) Inpatient Hospital and Rehabilitation Utilization Data Sheet
- 23) Long term follow-up phone questionnaire (2, 3, 4, and 5 years)

b. Study endpoints.

Subjects will be followed for 5 years. The primary endpoint will be the 1-year change in SF-36 physical component summary score (PCS) at one year. Secondary endpoints will include the 1-year change in mJOA, NDI, and EuroQol-5D scores as well as the observed complication rates, health service utilization, work status, and sagittal balance measurements.

c. Statistical Methods.

Primary analyses will include all subjects randomized using an intent-to-treat approach. The primary endpoint is the 1-year change in Physical Component Summary of the SF-36 (SF-36 PCS) at one year. A likelihood-based analysis using a mixed model will be used to compare SF-36 PCS between groups. This model will adjust for baseline SF-36 PCS, as well as study surgeon using a random effects model. All time points will be included in the model, and each subject will contribute data for the time points at which they were assessed. The model enables a statistical comparison between treatment groups at each time point, though the comparison at the one-year time point will be the primary analysis. The primary advantage of the mixed model, when compared to commonly used methods such as complete case analysis and single imputation (e.g. last observation carried forward), is its flexibility in handling missing data. This analysis will assume that missing data occurs at random (i.e. the missing data value can be dependent on observed data, but independent of unobserved

data). The inclusion of all follow-up time points in the model as well as covariates identified to be associated with withdrawal will assist in meeting this assumption and minimizing the risk of bias. Although the assumption for missing data is weaker under the likelihood based analysis compared to complete case analysis, a non-ignorable missing data mechanism is possible. Sensitivity analysis using selection and pattern mixture models will be employed to evaluate the robustness of conclusions to the missing at random (MAR) assumption.

Analysis Plan for Year 2 Outcomes

Year 2 outcomes for SF-36 and other continuous outcomes will be analyzed using linear mixed effects models (lme) that include both first and second year outcomes. The outcomes will be change from baseline. The purpose of the lme is to address missing second year outcomes. Since the year 2 assessments were missing mainly for logistical reasons (at 2 sites, research staff neglected to follow up with participants during specific time intervals), the missing at random (MAR) assumption of the lme is valid. The model will include treatment group, time period, and group*time interaction. To address within-subject correlation, patient id will be a random effect. There will be no adjustment for surgeon, since some surgeons had few patients, and no adjustment for baseline variables, since these were similar between groups. The treatment effect at year 2 will be tested using model contrasts. The year 1 treatment effect will be tested similarly, to confirm previous analyses obtained by t-test and anova. The models will be used to compare the 2 randomized groups and the “as treated groups.” We will not address multiple comparisons for the “as treated” analyses because they are considered to be exploratory.

Analysis Plan for Return to Work

The return to work analysis will include all time periods up to 12 months (1, 3, 6, and 12 months). Groups will be compared via Kaplan-Meier plots and log-rank tests. To address multiple comparisons when comparing the as-treated groups pairwise comparisons will be performed at $p=0.025$ to account for 2 comparisons (DL vs DF and DL vs VF).

Analysis Plan for Cost-Effectiveness

The research team has extensive experience conducting economic evaluations, including assessment of musculoskeletal interventions alongside RCTs and will conduct the proposed patient-oriented health resource utilization analysis. We will collect health resource utilization data as well as health cost data alongside this RCT.

Cost Analysis

Costs will be estimated for each patient from a societal perspective from the sources listed below, including only patients from the United States. A one-year time horizon will be selected to align with the primary outcome measure of the CSM-S Trial.

A. Index Hospitalization Costs:

- Hospital Costs: Total hospital charges (TotalHC) will be used to estimate costs using hospital-specific and year-specific Medicare cost-to-charge ratios (CCR). The costs will be adjusted for inflation to the current year without a 3% discount.
 - As a sub-analysis, hospital charges for specific revenue-centers (i.e., radiology, pharmacy, physiotherapy and occupational therapy) will be converted to costs using hospital-specific and year-specific Medicare CCRs. This will allow the identification of the major drivers of the difference in cost between the surgical strategies. A crosswalk between the revenue center and the cost center will be created.
- For professional services (identified with either HCPCS code or CPT-4 codes) provided to patients during the index hospitalization, costs will be calculated using national reimbursement amounts from the appropriate Medicare fee schedules for the respective year and site.

B. One-Year All-Cause Costs:

- One-year total hospital charges will be utilized in this part of the analysis. These include major health resource utilization events in the year following surgery including readmission, reoperation, injections, advanced imaging, and physical therapy.
 - Year-specific, site-specific Medicare cost-to-charge ratios, will be used to determine one-year costs from charges. These costs will be inflation adjusted. Professional services will also be included (identified with either HCPCS code or CPT-4 codes) and costs will be calculated using national reimbursement amounts from the appropriate Medicare fee schedules for the respective year and site.

C. Costs Due to Lost Productivity:

- We will assume that work was halted for patients on the procedure date.
- Lost wages will be estimated according to patients' occupations using the median weekly earnings in the US (for the current year) as reported by the Bureau of Labor Statistics.

- Lost wages for retirees will be valued at 65% of an employed patient and based on time to return to normal activities, which will be assumed to be three months

Hospitalization costs and one-year all-cause costs (total direct costs) will be combined with costs due to loss of productivity (indirect costs) to estimate total costs of each surgical procedure from a societal perspective.

Statistical Analysis Plan: The three cost outcomes will be reported in US Dollars and inflation-adjusted to the current year using the Gross Domestic Product Implicit Price Deflator. We will provide the descriptive statistics for the three outcomes (mean, median, standard deviation or SD, interquartile range, minimum, and maximum). Given that the cost outcomes are expected to follow a skewed distribution (non-normal), we will use generalized linear modeling (GLM) with Gamma distribution and a logarithmic link for cost. Any baseline patient characteristics found to be imbalanced between the cohorts will be adjusted for in the GLM. The mean predicted costs for each cohort and the differences in those predicted costs along with the 95% confidence intervals will be generated. If 10% or more of the overall study population has zero costs for the 1-year outcome, two-part modeling will be implemented. This will utilize a logistic regression to predict the presence of positive costs and a GLM model to predict non-zero costs as described above.

Calculation of Utility and Quality-Adjusted Life Years (QALY) Gained

- EQ-5D health-related quality-of-life questionnaires have been collected at baseline, 3 months, 6-months, 1-year, and 2-years. 1-year data will be used for cost-utility analyses.
 - For patients without complete data (i.e., without responses at all time points in the first year), we will assume missingness at random (MAR) and multiple imputation will be performed.
- Patient responses to the EQ-5D instrument will be mapped to utilities using the U.S. population value set and QALYs will be calculated for cost-utility analysis assuming a linear relationship between consecutive survey timepoints.

Incremental Cost-Effectiveness Ratio (ICER)

- The ICER will be calculated in a three-way extended dominance analysis, comparing each surgical treatment to the others. If a surgical procedure is both less costly and provides higher QALYs gained, that treatment will be dominant

over the others.

- A comparison of anterior and posterior approaches (namely, grouping the two posterior procedures) will be performed independently from the ICER model.
- Probabilistic analysis will be performed to account for sampling variation around ICER point estimates.
- Cost/QALY gained will be reported for each surgical treatment and for each approach.

d. Power Analysis.

Sample size for Specific Aim #1a (Ventral surgery is associated with superior SF-36 PCS outcome at one year compared to dorsal (fusion or laminoplasty surgery):

Sample size estimates were calculated based on analysis of covariance model with $\alpha = 0.05$ at 80% and 90% power using Power Analysis and Sample Size software (PASS 2008, NCSS, LLC. Kaysville, Utah). The primary endpoint is the SF-36 PCS. This component of the SF-36 is derived from the sums of scores of 21 items and thus exhibits distributional behavior commensurate with assumptions for parametric analysis. Our preliminary data suggest standard deviations for SF-36 PCS between 10 and 12 and correlations of baseline with one year SF-36 PCS between 0.6 and 0.7. *The following table describes the total sample size (2:3 ventral-dorsal randomization) required to detect a five point difference in SF-36 PCS one year post-surgery for various combinations of power, standard deviation and one year correlations under a fixed design.*

A minimum sample size of **137** patients provides at least 90% power (see Tables below):

Surgery (N)	Pre-op	Post-Op	Correlation between Pre- and Post-Op	Difference
Ventral (45)	35.5 ± 10.3	44.2 ± 11.7	0.64	+ 8.7 ± 8.2
Dorsal (70)	35.8 ± 11.3	39.8 ± 11.6	0.66	+ 4.0 ± 9.5
Dorsal Fusion (42)	35.0 ± 11.7	39.6 ± 12.4	0.65	+ 4.6 ± 10.0
Laminoplasty (28)	37.0 ± 10.9	40.1 ± 10.6	0.67	+ 3.1 ± 8.8
All patients (115)	35.7 ± 10.9	41.5 ± 11.8	0.64	+ 5.8 ± 9.7

Difference / SD	Correlation	80% Power / 5% Type I error (2-sided)			90% Power / 5% Type I error (2-sided)		
		N _{Ventral}	N _{Dorsal}	N	N _{Ventral}	N _{Dorsal}	N

5 / SD = 10	0.60	38	56	94	50	74	124
5 / SD = 10	0.65	40	59	99	53	78	131
5 / SD = 10	0.70	42	62	104	55	82	137

The sample size will be inflated by 5% to accommodate multiple significance testing using an O'Brien-Fleming stopping boundary. Based on our preliminary data and pilot studies, withdrawal and loss-to-follow-up are not expected to be high. The sample size will be further inflated by 10% to accommodate attrition during the follow-up. Thus, 159 total patients will be recruited and randomized. **Ten high volume surgeons/ centers with the necessary expertise to permit patient randomization (16 randomized CSM cases/ site) have been selected to achieve the goal of enrolling 159 randomized patients over 18 months. An additional 91 nonrandomized patients will be enrolled into the study.**

Sample size for Specific Aim #1b (Compared to pre-operative baseline status, both ventral and dorsal surgery for CSM improve symptoms of spinal cord dysfunction at one year follow-up):

Using the sample size estimate for Specific Aim #1a and assuming ~10% attrition during follow-up, we expect to have 55 ventral surgery and 82 dorsal surgery patients (total = 137 patients) available for analysis. We will be able to detect changes from baseline pre-operative mJOA status as small as 2.0 points (clinically important difference) for both the ventral surgery cohort and the dorsal surgery cohorts at one year. Assumptions for this sample size analysis include Type I alpha = 0.025, power at 90%, and range of within-subject correlation of 0.60 to 0.70.

H. Economic Considerations

No subject will incur any additional cost for participating in this study. All of the pre- and post-operative CT, MRI, flexion-extension x-rays, and pre-operative sagittal balance films are considered standard of care. The post-operative sagittal balance films, which only randomized patients will receive, are not considered standard of care and will be billed directly to the research fund. All costs associated with the administration of the study will be assumed by the Patient-Centered Outcomes Research Institute (PCORI) and/or the Lahey Comparative Effectiveness Research Institute.

[figure not shown]
III. HUMAN SUBJECTS

A. Subject Population, Recruitment

Eligibility Criteria: Patients aged 45-80 years with CSM (≥ 2 levels of spinal cord compression from C3 to C7) presenting with ≥ 2 of the following symptoms/signs: clumsy hands, gait disturbance, hyperreflexia, up going toes, bladder dysfunction.

Exclusion Criteria: Any of the following: C2-C7 kyphosis $> 5^\circ$ (measured in standing neutral cervical spine radiograph), segmental kyphotic deformity (defined by ≥ 3 osteophytes extending dorsal to a C2-C7 dorsal-caudal line measured on cervical spine CT), structurally significant ossification of posterior longitudinal ligament (OPLL – measured on cervical spine CT), previous cervical spine surgery, or significant active health-related co-morbidity (Anesthesia Class IV or higher).

EXCLUDE

INCLUDE

**Segmental-Cervical
Kyphotic Deformity**

Yes

No

Figure. Two cases with sagittal CT reconstructed images are depicted. A line is drawn from the dorsal caudal point of C2 to the dorsal caudal point of C7. If 3 or more levels of disc-osteophyte extend dorsal to the line, then the case has a segmental-cervical kyphotic deformity and the case would be excluded from the study. The C2-C7 Cobb angle is 5 degrees lordosis in both cases

Subjects will be enrolled by participating spine surgeons who are investigators in the study. These subjects will be identified within the existing practice of each surgeon. There will be no advertising or any effort to recruit subjects into the study from outside the practice of a study surgeon investigator.

Once a patient has been screened, identified as having CSM, and agreed to participate in the trial by signing consent, the subject will undergo two reviews. The patient's images will first be reviewed by a Central Review Committee ([name] and [name]) to confirm eligibility. If the patient is deemed eligible, their images will then be reviewed by the spinal experts network. The patient's images will be uploaded onto the web-based platform, and an email will be generated and sent to all 15 members (15 CSM surgeon investigators) of the spinal experts panel. Each surgeon will be asked to vote: 'randomize' or 'do not randomize' and then to characterize his/her preferred surgical approach as **ventral** or **dorsal**. If after 72 hours, a majority (>50%) of the review panel (with at least 9 votes for a quorum) favor randomization (equipose) and less than 80% select one approach (ventral or dorsal) over another, then the patient will be eligible for study randomization.

The results of the voting (the number of votes randomize or do not randomize and the number of ventral or dorsal votes) will be available to the patient both to increase patient trust and confidence in the recommendation for randomization, as well as to protect patients from undergoing randomization when one approach (ventral or dorsal) might be superior for that patient.

Patient Randomization (See Figure 1 Below)

[figure not shown]
Patients will be offered randomization in a subsequent one-hour meeting (following spinal experts review of the case) among study coordinator, surgeon, and patient if two conditions are met:

- 1) Central Review Committee ([name] and [name]) checked the images and clinical exam findings and found the patient eligible; and
- 2) Spinal Experts Panel confirmed patient's eligibility (>50% majority vote "randomize" and less than 80% select one approach (ventral or dorsal) over another).

The patient can either consent to or decline randomization. There will be two categories of patients who have signed an IRB-approved consent to participate in the study:

1. Randomized cohort: Upon confirmation of eligibility and patient acceptance of randomization, the study coordinator will access the assignment by logging into the secure website (<https://pip.acesis.com>) with a password and will obtain the randomization assignment from the web-based platform with its pre-programmed blocked (2, 4, or 6 subjects/block) stratified site-specific randomization scheme. Randomized patients will be followed for five years.
2. Non-Randomized cohort: The non-randomized cohort will consist of all patients who meet entry criteria but for whom equipose is not confirmed by spinal experts panel. It also will consist of patients who do not consent to randomization. All non-randomized patients will be asked to complete all the study questionnaires and will be followed for five years. The non-randomized cohort will not have an independent radiologist evaluation.

Figure 1 Randomization Procedure

B. Source of Research Material

Subjects will be identified from within the practice of spine surgeon investigators.

C. Consent Procedures

Subjects will be identified by investigator spine surgeons within their practice. Subjects will be registered by the surgeon's office. The subjects will be clearly told by the surgeon that participation is voluntary and that a decision not to participate will not affect their medical care in any way. The patient will sign a consent form with the spine surgeon after having a chance to review the study protocol and consent form with family and others. The subjects will sign the consent with the surgeon during a separate office visit prior to surgery. A spine study coordinator will then contact the patient for more detailed questions regarding registration for the study (e.g. home phone number and home address). The study coordinator will also ask the patient whether he is comfortable enrolling in the study.

D. Risks

All of the subjects in the study will be surgical candidates and would have had surgery recommended even if they were not involved in a study.

E. Protection of Subjects

All subjects will receive standard follow-up by the treating surgeon. All of the surgical procedures are considered standard care and none are considered investigational. The results will be made available to the subjects prior to publication. Any significant findings regarding the overall safety of either procedure at any site will be brought to the attention of all subjects in the study once all of the appropriate IRB committees have been notified. The confidentiality of all subjects will be assured by assigning all subjects a code and by removing all identifying information from questionnaires. Data entered into the study web site will be encrypted using the current industry standard to protect patient confidentiality.

Once the database is analyzed, all patient identifiers will be removed from the final database. The database will be kept at the Lahey Comparative Effectiveness Research Institute. No patient identification would be linked to the data.

F. Data and Safety Monitoring Plan

(As outlined above in Research Plan)

G. Confidentiality

Each subject will be assigned a code number and no identifying information will leave the Lahey Comparative Effectiveness Research Institute. Data from each patient will be sent to the Lahey Comparative Effectiveness Research Institute or will be entered into the study web site which is encrypted to protect patient confidentiality using the current industry standard. All patient identifiers will be removed from the final database.

H. Potential Benefits

Subjects will be followed closely and might gain from the increased observation. Each subject will be offered a free review of their radiographic images by a panel of spinal experts. The multiple opinions from other surgeons will be used to help educate subjects about their condition. The subjects will have the opportunity to learn about the results of the study through frequent updates available from the Lahey Comparative Effectiveness Research Institute or from the public web page (<https://pip.acesis.com>).

Society at large might benefit from the results of this study. The study will be useful for spine surgeons to determine if health resource utilization differs among the three surgical procedures for people with cervical spondylotic myelopathy.

I. The Risk-Benefit Ratio

All subjects entered into the study would be surgical candidates for either surgical procedure in the study. All of the surgical procedures used in this study are routine and constitute standard care. No procedure is considered investigational. Therefore, no subject will have any increased risk of physical injury as a result of participation in the study. The subjects will have access to the Study website and will be informed of the results of the study prior to publication. The increased level of observation will possibly benefit some of the subjects. The subjects will know that they are helping society at large because the results of the study will be useful for spine surgeons to help future subjects determine which surgical procedure is best for people with cervical spondylotic myelopathy.

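### The Year 2 model leaves out the 3- and 6-month scores and the baseline covariate, and has no sensitivity analysis for MAR, although its stated purpose is to deal with missing Year 2 data

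*Combined protocol and SAP*

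**What the plan says.** Section II.G.c describes two mixed models.

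**Primary (Year 1) analysis, Statistical Methods.**
- Visits: "All time points will be included in the model, and each subject will contribute data for the time points at which they were assessed".
- Covariates: "This model will adjust for baseline SF-36 PCS, as well as study surgeon using a random effects model".
- Support for MAR: "The inclusion of all follow-up time points in the model as well as covariates identified to be associated with withdrawal" are said to help meet the assumption and limit bias.
- The plan concedes that "a non-ignorable missing data mechanism is possible", and adds: "Sensitivity analysis using selection and pattern mixture models will be employed to evaluate the robustness of conclusions".

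**Analysis Plan for Year 2 Outcomes.**
- Visits: "linear mixed effects models (lme) that include both first and second year outcomes", analysed as change from baseline.
- Terms: treatment group, time, their interaction and a patient random effect. Surgeon is dropped because some surgeons had few patients. Baseline variables are dropped because the groups were similar.
- Missing data: the losses are put down mainly to research staff at two sites who did not follow patients up in certain intervals, and from this the plan concludes that "the missing at random (MAR) assumption of the lme is valid".
- No sensitivity analysis is named.

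The list of data sheets in Section II.G.a schedules SF-36, NDI and EQ-5D at 3 and 6 months as well as at Years 1 and 2.

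**The concern.** The Year 2 model exists to handle missing data, yet it conditions on less than the plan's own primary analysis does. A patient seen at 3 and 6 months but not at Years 1 or 2 contributes nothing to it. Baseline enters only by subtraction, and there are no covariates related to withdrawal.

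The argument for MAR is also incomplete. The word *mainly* admits other reasons for missing data, which are not described or tested. The primary analysis treats a non-ignorable mechanism as possible and tests for it, whereas the Year 2 section asserts MAR and stops. At stake are some avoidable loss of precision in the Year 2 contrast, a possible bias if early scores drive missingness differently in the two arms, and a Year 2 conclusion with no stated robustness to departures from MAR.

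**Working it through.** The plan gives no Year 2 missingness rate, standard error or power, so there is no figure to reproduce. The steps below size the effect under stated assumptions.

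**1. Precision lost by omitting 3 and 6 months**

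From the documents: 159 randomised at 2:3, so 159 × 2/5 ≈ 64 and 159 × 3/5 ≈ 95; SD of change 9.7 (pilot table, all patients, Section II.G.d). Assumed: equal between-visit correlation ρ = 0.65; 25% missing at Year 2 and 10% at Year 1, independently; 3 and 6 months complete.

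The variance of the contrast is σ²(1/64 + 1/95) × [I⁻¹] at Year 2, where I sums, over missing-data patterns, the pattern probability times the inverse correlation matrix of the visits seen.

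- Patterns: both visits 0.90 × 0.75 = 0.675; Year 1 only 0.225; Year 2 only 0.075; neither 0.025.
- 1/(1 − 0.65²) = 1.7316, and 0.65 × 1.7316 = 1.1255.
- Year 1 diagonal: 0.675 × 1.7316 + 0.225 = 1.3938. Year 2 diagonal: 0.675 × 1.7316 + 0.075 = 1.2438. Off-diagonal: −0.675 × 1.1255 = −0.7597.
- [I⁻¹] at Year 2 = 1.3938 / (1.3938 × 1.2438 − 0.7597²) = 1.205.
- Variance = 94.09 × 0.02615 × 1.205 = 2.966, so SE = 1.722.
- The same formula with all four visits gives SE = 1.683. The variance ratio is (1.722/1.683)² ≈ 1.047.

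Over ρ 0.5-0.75, Year 2 missingness 15-35% and Year 1 missingness 7-15%, the ratio is 1.02-1.08. If everyone missing at Year 1 is also missing at Year 2, it is 1.03-1.13.

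**2. Precision lost by omitting baseline as a covariate**

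Inputs: 55 and 82 analysable patients and SD 10 (Section II.G.d); correlation 0.65, inside the plan's 0.6-0.7 for baseline with one year and assumed equal for all pairs of visits. Assumed: 30% missing at Year 2, half of them also missing at Year 1.

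| Model | SE of Year 2 contrast |
|---|---|
| As planned (change scores, two visits) | 1.70 |
| Baseline covariate added, two visits | 1.56 |
| Baseline covariate, 3 and 6 months added | 1.52 |

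Across the correlation structures and missingness rates checked (10-40% at Year 2), dropping baseline raises the variance by 16-34%, and dropping the early visits by 0-10%.

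**3. Bias when missingness depends on the 6-month result**

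Assume that in one arm only the log-odds of being lost fall by 0.8 per SD of the 6-month change. Let m be the mean standardised 6-month change among patients who stay: m = 0.075 at 10% lost and 0.139 at 19% lost.

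- *Years 1 and 2 both lost:* bias = σρm. At 10%, 9.7 × 0.5 × 0.075 = 0.36 and 9.7 × 0.65 × 0.075 = 0.47. At 19%, 0.67 and 0.87; simulation gave 0.69 to 0.91.
- *Year 1 seen, only Year 2 lost:* bias ≈ σ(ρ − ρ²)m, which is about 0.17-0.18 at 10% and 0.31-0.34 at 19%.
- *Both arms affected, 12% against 8%, Years 1 and 2 lost:* 0.14-0.18.
- *Both arms affected equally:* 0.

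A four-visit model has a bias of about 0 in the one-arm dropout scenario, because the 6-month result is then in the model. A separate check let the 6-month score itself drive missingness in one arm (1 logit per SD; 28-29% missing there, 25% in the other arm). The planned model was biased by about −0.4 with correlation decaying over time and about 0 with equal correlation. The four-visit model was unbiased in both.

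**4. Missingness that depends on the unseen Year 2 score**

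In that same set-up, both models are biased: 0.7-1.2 points for the planned model and 1.0-1.7 for the model with baseline and all visits. Early visits do not repair this, so a sensitivity analysis is needed.

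**The case against.** The strongest reply is that the plan names a concrete cause. Staff at two sites failing to follow patients up has no stated link to scores, and such a lapse does not bias either model. A likelihood model for Years 1 and 2 is a legitimate MAR analysis, and the precision lost by omitting early visits is small. All of this stands. What it does not cover is the remainder behind *mainly*.

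Several stronger readings are tempting, and the documents do not support them.

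- *The Year 2 contrast is biased by 0.7-0.9 points.* That needs about 19% lost before Year 1, driven by the 6-month result, in one arm only. Nothing in the documents suggests this, and Section II.G.d plans for about 10% attrition.
- *Losing data at two sites biases the randomised comparison because site is not in the model.* Randomisation is blocked and stratified by site (Section III.A), so a site-level lapse falls on both arms. Bias would need losses that differ by arm, or a treatment effect that varies by site. The as-treated comparison lacks this protection, but the plan calls it exploratory.
- *The main result of the trial is affected.* Section II.G.b lists 1-year score changes as endpoints and no Year 2 score. The 5-point target is also a one-year figure.

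Two further points bear on the comparison with Year 1. The primary model, with all time points and a group comparison at each, could be read as already yielding a Year 2 contrast, but the specific Year 2 section displaces that reading. And the Year 2 section refers to Year 1 results obtained by t-test and ANOVA, so the Year 1 standard used here is the written plan and may not be what was done.

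**Conclusion.** The point holds in a limited form. As written, the Year 2 analysis falls below the plan's own written Year 1 approach in three respects: it omits early visits already scheduled for collection, it drops the baseline covariate, and it does not test MAR.

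Omitting the early visits costs about 2-8% in variance under the assumed missingness; omitting baseline costs more. Bias is conditional on score-related missingness that differs between arms: roughly 0.2-0.5 PCS points in moderate one-arm scenarios, up to about 0.9 in an extreme one, and none from the stated staff lapse. These sizes rest on assumed missingness rates, correlations and dropout slopes, because the documents give none for Year 2. The missing sensitivity analysis is the more consequential gap, since no choice of visits replaces it. This is worth correcting but does not threaten the primary 1-year analysis.

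**What to change.** 1. Fit one likelihood-based model to the 3-, 6-, 12- and 24-month scores, with group-by-visit terms, unstructured within-patient covariance, the baseline score and site (the randomisation stratum). Test the Year 2 contrast from that model. Similar baselines are no reason to omit the baseline score, because its main gain here is precision. The plan's reason for dropping surgeon, few patients each, applies less to site, where 16 randomised cases per site were planned.
2. Separately, extend the pattern mixture analysis already planned for Year 1 to Year 2.
3. Report Year 2 missingness by arm, site and reason, so that the statement about logistical causes can be checked.
4. Reconcile the planned Year 1 mixed model with the reference to earlier t-test and ANOVA results.

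The cost is SAP wording, a little more analysis work and a few more covariance parameters. No new data are needed.
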